Effect of Whole Body Vibration Therapy on Muscle Function, Gross Motor Function and Bone Mineral Density in Children with Spinal Muscular Atrophy - a Feasibility Study

NCT number: NCT03056144

Document date: August 1, 2018

Effect of Whole Body Vibration Therapy on Muscle Function, Gross Motor Function and Bone Mineral Density in Children with Spinal Muscular Atrophy - a Feasibility Study

Abstract

Spinal muscular atrophy (SMA) are one of the common physical disabilities in childhood. For SMA, progressive muscle weakness and early fatigue hamper the mobility of the sufferers. Osteopenia is common for this population group due to poor bone growth and muscle disuse. As a result, non-traumatic related fractures and bone pain are common. Recently, whole body vibration therapy (WBVT) has been proven to improve bone health and muscle function in healthy adults and post-menopausal women. Among the limited studies on the WBVT for children with muscular dystrophies, promising results have been shown on gross motor function, balance, and muscle strength and the WBVT appears to be safe for children with SMA.

The present pilot study is designed to investigate if WBVT is safe and feasible for individuals with SMA and if WBVT can improve muscle function, functional abilities, postural control and bone mineral density in children with SMA. Convenience samples of 10 individuals with SMA type III will be recruited. The participants will receive the WBVT of 25 Hertz and a peak-to-peak amplitude of 4mm for a session of about 18 minutes, 3 days per week for 4 weeks. Assessment will be performed at the baseline and the completion of the intervention to examine the muscle function, functional abilities, postural control and bone mineral density of the participants.

It is anticipated that the outcomes of this pilot study for SMA may show if this intervention is safe, feasible and beneficial for children with SMA type III regarding to muscle function, functional abilities, postural control and bone mineral content and if there may be any related practical issues of this intervention to this population group. The outcomes also provide research evidence to clinicians if this intervention should be recommended to individuals of similar problems.

Objectives

The objective of the present pilot study is to investigate if the WBVT is able to improve the muscle strength, functional abilities, postural control, and bone mineral density in children/adolescents with SMA type III.

Null hypotheses to be tested:

1. That there is no statistically significant difference in gross motor function as measured using the North Star Ambulatory Assessment (NSAA) pre- and post-intervention.
2. That there is no statistically significant difference in functional abilities as measured using Pediatric Evaluation of Disability Inventory (PEDI) pre- and post-intervention.
3. That there is no statistically significant difference in postural control as measured using Segmental Assessment of Trunk Control (SATCo) pre- and post-intervention
4. That there is no statistically significant difference in sub-maximal exercise capacity as measured using the 2-minute walk test (2MWT) pre- and post-intervention.
5. That there is no statistically significant difference in body composition and bone mineral density as measured using dual X-ray absorptiometry (DXA) pre- and post-intervention.

Methodology

This feasibility study aims to examine the safety of the WBVT on children with type III SMA.

Children with type III SMA are targeted as they have adequate independence living in the community but still experience early fatigue during normal level of exercises due to the nature of their condition. They are at high risk of suffering from complications due to compromised mobility such as osteopenia, early loss of ambulation when compared with their healthy peers.

Intervention protocol

The WBVT will be performed on the Galileo™ Med L Plus (Novotech Medical GmbH) with the study participants standing with both knees flexed at least 20 degrees. The vibration frequency and duration will be increased over 5 days to the maximum of 3 minutes of 24 to 25 Hz with a peak to peak amplitude of 4mm. The participants of the intervention group will undergo the WBVT 1 session per day, 3 days per week for 4 weeks. The whole WBVT session will last 18 minutes with 9 minutes of vibration. This intervention regime is based on the recommended dosage to improve bone mineral density in children with physical disabilities in a systematic review on previous relevant literature (Matute-Llorente et al 2014). The intervention regime is as follows:

Day	Vibration 1	Rest 1	Vibration 2	Rest 2	Vibration 3	Rest 3
1st	1 min; 12Hz	3 min	1 min; 12Hz	3 min	1 min; 15Hz	3 min
2nd	1 min; 15Hz	3 min	1 min; 15Hz	3 min	2 min; 15Hz	3 min
3th	2 min; 15Hz	3 min	3 min; 15Hz	3 min	3 min; 15Hz	3 min
4th	2 min; 24-25Hz	3 min	2 min; 24-25Hz	3 min	2 min; 24-25Hz	3 min
>5th	3 min; 24-25Hz	3 min	3 min; 24-25Hz	3 min	3 min; 24-25Hz	3 min

The participants will perform mini-squats (knee flexion from 20 to 40 degrees) during Vibrations 1 and 3 and weight-shifting between right and left legs during Vibration 2 on the vibration platform under the supervision of a research assistant, who will be trained by the PI prior to the commencement of the study. All treatment sessions will be conducted at the Hong Kong Polytechnic University Rehabilitation Clinic as most of children and adolescents with SMA study in main-stream schools in Hong Kong.

Participants:

10 children with type III SMA aged from 6 to 18 years will be recruited. The age range is extended aiming to increase the number of recruitment due to the rarity of the condition. All participants will continue their usual intervention regime, if any, during the study period. They are strongly encouraged not to participate any activities that may involve any total body vibration during the study period.

Inclusion criteria:

To be included in the study, children must:

1. Be able to stand on the vibration platform without support;
2. Be able to undertake clinical examination and DXA evaluation; and
3. Informed consent by the participant’s parent/ guardian.

Exclusion criteria:

1. There is a history of fracture within 8 weeks of enrolment of the present study and acute thrombosis, muscle or tendon inflammation, renal stones, discopathy or arthritis as reported by

their parent/ guardian.

2. There is a history of using any of the following medications, regardless of dose, for at least 1 month, within 3 months of enrolment into the present study: anabolic agents or growth hormone.

Outcome measures:

Assessments will be performed at baseline and after 4 weeks of the intervention. All outcome measures will be conducted on all study children, unless specified to children with specific diagnoses. They include:

1. Muscle strength

a) hand-held dynamometer will be used to measure muscle strength in hip flexors, hip extensors, hip abductors, knee extensors, knee flexors, ankle plantarflexors and dorsiflexors in standardised muscle testing positions (Clarkson and Gilewich 2000). Muscle strength will be reported in kilograms.

2. Functional abilities

a) North Star Ambulatory Assessment (NSAA) will be used to examine the gross motor function of the participants (Mayhew et al 2011, Scott et al 2012).

b) 2-minute walk test (2MWT) will be used to assess submaximal exercise capacity (Pin 2014, Pin and Choi 2016). Distance covered in 2MWT will be measured by a distance-measuring trundle wheel in metres.

c) Range of movements in hip flexion, extension and abduction, knee flexion and extensions and ankle dorsiflexion and plantarflexion will be measured in standardised positions (Clarkson and Gilewich 2000).

d) Segmental Assessment of Trunk Control (SATCo) to assess the segment trunk control (Butler et al 2010).

e) Pediatric Evaluation of Disability Inventory (PEDI) (Haley et al 1992) to assess functional capacities in the domains of daily activities, mobility and social/cognitive function. A validated Chinese version will be used (Chen et al 2009).

3. Bone mineral density

a) Dual Energy X-ray Absorptiometry (DXA)- bone mineral content (BMC) and areal bone mineral density (aBMD) of the distal femur and total body will be measured. *Only if* it is not feasible to obtain the BMC and aBMD of the femur, BMD of the lumbar spine will be used. The effective radiation dose for these DXA studies will be <2 microSv, which is a very minimal dose of radiation (Houlihan and Stevenson 2009). All participants will have DXA done in a private service as bone density examination is not routine for the children with motor disabilities in Hong Kong.

b) Anthropometry at baseline and 4 weeks including standing height and weight. Body mass index (BMI) will be calculated and converted into a z-score.

4. Parental satisfaction

a) Parental/ participant questionnaire to record present medications of their children, satisfaction or comments on the intervention regime by children/ parents of the intervention group.

b) Visual analogue scale of 0 to 10, in which 0 means no pain and 10 as extreme pain to assess pain or discomfort at rest and if any, pain or discomfort associated with the intervention as reported by the children and/or parents.

c) A log of compliance and comments during the intervention.

Statistical analysis plan

Due to the small sample size, non-parametric tests will be used to analyse the results. All results will be reported in means and standard deviations. Wilcoxon Signed test will be used to

compare all the outcome measures listed above (no. 1 to 3) before and after the intervention. Results of outcome measure no. 4 listed above will be reported in descriptive terms for the comments from the parents and/or from the participants and compliance/ comments during the intervention and Wilcoxon Signed test will also be used to compared the visual analogue score of discomfort before and after the intervention.

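### The Objectives ask whether WBVT improves outcomes, but an uncontrolled before/after sample of 10 can only describe change, not attribute it to WBVT

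*Combined protocol and SAP*

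**What the plan says.** The Objectives section of the combined protocol and SAP is a single sentence: the aim is "to investigate if the WBVT is able to improve the muscle strength, functional abilities, postural control, and bone mineral density" in children and adolescents with SMA type III. The Abstract adds that the outcomes will "provide research evidence to clinicians if this intervention should be recommended to individuals of similar problems".

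The design is described as follows:

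- **Sample (Abstract):** "Convenience samples of 10 individuals with SMA type III will be recruited". Every participant receives WBVT.
- **Concurrent care (Participants):** "All participants will continue their usual intervention regime, if any, during the study period".
- **Timing (Outcome measures):** "Assessments will be performed at baseline and after 4 weeks of the intervention".
- **Analysis (Statistical analysis plan):** Wilcoxon signed-rank comparisons of before with after, for outcome groups 1 to 3 and for the pain scale.

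The five null hypotheses are all worded as pre/post differences. They cover NSAA, PEDI, SATCo, the 2-minute walk test and DXA.

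On safety and feasibility, the title calls this a feasibility study, the Abstract says it "is designed to investigate if WBVT is safe and feasible for individuals with SMA", and Methodology says "This feasibility study aims to examine the safety of the WBVT on children with type III SMA". The Objectives sentence mentions neither.

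**The concern.** Asking whether a therapy is able to improve an outcome is a causal question. It needs some account of what would have happened over the same 4 weeks without the therapy, and the plan has none. The hypotheses and tests answer a different and narrower question: did the scores of these children differ between two dates?

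If the two are treated as the same, a significant Wilcoxon result could be read as showing that WBVT works and a non-significant one as showing that it does not, and either could reach clinicians as evidence on recommending it. Neither reading is sound. The Abstract itself notes that in SMA "progressive muscle weakness and early fatigue hamper the mobility of the sufferers", so the untreated course may be downward. Stable scores could then hide a benefit, just as growth or familiarity with the tests could imitate one.

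**Working it through.** **1. Is there any contrast that isolates WBVT?** Setting the sections side by side:

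| Question | What the plan provides |
|---|---|
| Untreated or alternative-treatment group? | None described; all 10 are treated |
| Allocation or between-group test? | None described |
| Untreated run-in or repeated baseline? | None; one baseline and one 4-week assessment |
| Other care withheld? | No; usual care continues |
| Planned comparison | After versus before, same children |

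The phrase 'intervention group' occurs in Intervention protocol and again under Parental satisfaction, but no second group goes with it.

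**2. What does the planned test estimate?** For child *i*, the observed change is

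D_i = (effect of WBVT)_i + (all other change over 4 weeks)_i + error_i.

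The signed-rank test concerns the centre of D. With one group and two time points, the first two terms enter only as a sum, so no p-value at any sample size separates them. The rival terms do not all have equal support. Disease progression and continuing usual care are in the documents. Growth is a reasonable expectation at ages 6 to 18, and practice or effort on performance tests (not DXA) is a possibility; the documents give no size for either.

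**3. How precise is the descriptive estimate?** The plan gives no power, effect size, SD or significance level, so it has no figure to reproduce. The interval matched to the signed-rank test is the Hodges-Lehmann interval.

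- Pairwise (Walsh) averages at n = 10: 10 × 11 / 2 = 55.
- The exact test rejects when the smaller rank sum is 8 or less. Of the 2^10 = 1,024 sign patterns, 25 give a rank sum of 8 or less in one tail, so the two-sided size is 2 × 25 / 1,024 = 0.0488.
- The matching interval runs from the 9th smallest to the 9th largest average, with coverage 1 − 0.0488 = 95.1%.
- Simulated mean half-width over 100,000 samples of 10 normal, untied changes: 0.713 SD of the change score.
- Order-of-magnitude check with the t interval when the sample SD equals the true SD: 2.262 / √10 = 0.715 SD.

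For whole-point scores with ties, coverage and width differ somewhat.

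**4. Which stated outcomes are tested?** Muscle strength comes first in the Objectives sentence and is outcome group 1, so the SAP tests it. None of the five null hypotheses mentions it.

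**5. What could the feasibility data show?**

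- Sessions: 3 per week × 4 weeks = 12 per child, or 120 for 10 children.
- If all 10 children complete, the exact (Clopper-Pearson) two-sided 95% lower limit is 0.025^(1/10) = 0.692, or 69%.

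The plan describes a log of compliance and comments but does not say that it records attendance or completion.

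**The case against.** The best defence is that this is an openly labelled pilot in a rare condition. The hypotheses and the SAP already speak only of pre/post difference, the Abstract says that the outcomes *may* show benefit, and no section states that a significant Wilcoxon result will be declared a WBVT effect. Much of this stands. Rarity is a fair reason for 10 children and one arm, and the misreading is a risk rather than a declared intention. But the Objectives sentence is causal as written, and the sentence on recommending the therapy carries no such hedge. No limit on causal interpretation is stated.

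It is also fair that care continuing unchanged need not itself produce a change, and that practice effects are not documented. This narrows the list of rival explanations without supplying a contrast that would exclude them.

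A reader might infer more than the documents support:

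- **That the trial has no safety or feasibility aim.** It does: the title, the Abstract and (for safety) Methodology state it. Adding it to the Objectives aligns the text; it does not repair an absent aim.
- **That a false-positive rate for benefit can be quoted.** Any such figure needs the size of the non-treatment shift, the SD of change and a significance level, and the documents give none. The argument does not need it.
- **That the exercises done on the platform invalidate the study because vibration alone cannot be isolated.** The protocol describes the session as one programme, and on that reading the point falls away.
- **That zero events in 10 children would bound a safety risk.** The plan describes no adverse-event recording, so such a limit would have no defined numerator.

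**Conclusion.** The concern holds as a mismatch between claim and design. The objective and the recommendation sentence claim more than a single-group before/after comparison can deliver, in either direction and whatever the p-value. This conclusion follows from the design and rests on no assumed number.

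The interval of about 0.71 SD either side is a secondary description of precision. It assumes 10 complete pairs with normal, untied changes. The 69% lower limit assumes that all 10 children complete.

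The data remain worth collecting and the planned tests remain usable as description. The sponsor should make the change before results are reported, because it alters what the trial may conclude. The documents do not support a demand for a control group, or a claim that safety and feasibility were overlooked.

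**What to change.** 1. **Efficacy objective.** Restate it as describing change from baseline in the same four areas over a 4-week WBVT programme, and say that the change will not be attributed to WBVT.
2. **Analysis.** Keep all the planned Wilcoxon tests, including the one for muscle strength that the five hypotheses omit, and label them exploratory. Beside the planned means and SDs, report each change as a Hodges-Lehmann estimate with its 95% interval.
3. **Abstract.** Qualify the sentence on recommending the therapy, so that the results inform whether a controlled trial is warranted.
4. **Consistency.** Bring the safety and feasibility aims into the Objectives, tied to the planned pain scale, comments and compliance log. Have the log record sessions attended out of 12 and whether each child completed. Report the completion proportion with an exact 95% interval.

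The cost is wording, two explicit entries in a log already planned, and intervals computed from the same data. No visit, assessment or participant is added, and no test is removed. The downside is a more modest efficacy claim, with intervals that will look wide at n = 10.

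### Safety and feasibility are stated aims but are missing from the Objectives and hypotheses; adverse events are not defined, systematically elicited or counted, and the SAP does not name the pain item it tests

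*Combined protocol and SAP*

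**What the plan says.** The Abstract puts safety and feasibility ahead of efficacy: "The present pilot study is designed to investigate if WBVT is safe and feasible for individuals with SMA". The Methodology section opens with safety alone: "This feasibility study aims to examine the safety of the WBVT on children with type III SMA". The Abstract anticipates that the results "may show if this intervention is safe, feasible and beneficial for children with SMA type III", and continues: "The outcomes also provide research evidence to clinicians if this intervention should be recommended to individuals of similar problems". It also says that in this population "non-traumatic related fractures and bone pain are common".

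The Objectives section asks only "if the WBVT is able to improve the muscle strength, functional abilities, postural control, and bone mineral density". The five null hypotheses cover the NSAA, PEDI, SATCo, 2-minute walk test and DXA, each compared before and after treatment.

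The data closest to safety and feasibility are in Outcome measures, item 4 (Parental satisfaction). They are a questionnaire, a 0 to 10 VAS with two items (pain at rest and, if any, pain linked to the intervention), and a log of compliance and comments. The Statistical analysis plan section reports the comments and compliance descriptively and applies a before/after Wilcoxon test to the discomfort score, without naming the item. A general sentence says that all results will be given as means and SDs.

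Sessions are given "1 session per day, 3 days per week for 4 weeks", and the exercises on the platform are done "under the supervision of a research assistant".

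**The concern.** A safety aim needs at least the number of children who had an untoward event, out of those exposed. Nothing in the plan is specified to produce that number. A free-comment log holds what someone volunteers or chooses to write down, so a blank entry cannot be read as a child who was asked and had no event. A fall or a fracture has no required field.

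The Abstract offers the results to clinicians as evidence on whether to recommend the therapy, in a population it describes as prone to fracture and bone pain. Events not asked about while sessions are running cannot be reliably recovered afterwards, so the gap has to be closed before data collection.

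**Working it through.** The documents give no event rate, alpha, power, sidedness or feasibility threshold, so there is no planned figure to reproduce. The check is a reading of the text, with some arithmetic on what a count would deliver.

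**1. Tracing each aim through the plan**

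| Place | Safety | Feasibility |
|---|---|---|
| Abstract | stated | stated |
| Methodology, opening | stated | in the study label only |
| Objectives | absent | absent |
| Null hypotheses 1 to 5 | absent | absent |
| Outcome measures, item 4 | pain VAS, comments | compliance log, questionnaire |
| Statistical analysis plan | VAS test and means/SDs; comments descriptively | compliance descriptively |

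No row contains an event definition, a schedule for asking, a severity or relatedness rule, or a count.

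**2. The tested VAS item**

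- Pain linked to the intervention has no value before the intervention, so it cannot enter a before/after pair over the course.
- Pain at rest has one. Outcome measures sets assessments at baseline and after 4 weeks, so a pair of rest scores can miss discomfort that arises in a session and resolves.
- The before/after wording could also mean each session. The assessment schedule makes the 4-week reading likelier, but the SAP does not settle it.

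**3. Why a mean cannot replace a count (assumed VAS changes)**

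Take 10 children with changes of +8 (one child), -1 (eight) and 0 (one). The mean is (8 - 8 + 0)/10 = 0.0 and the SD is √[(64 + 8)/9] = 2.8, yet one child reached at least 8. The SD would hint at an outlier, but it would not say how many children were affected.

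**4. What the Wilcoxon test could show**

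With m non-zero changes, the smallest exact two-sided p is 2/2^m: 0.25 for m = 3, 0.0625 for m = 5 and 0.031 for m = 6. If most children score 0 both times, the test could not reach an assumed 0.05 level, so non-significance would not be evidence of safety.

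**5. What a count would give (n = 10, exact Clopper-Pearson 95%)**

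- 0/10: the upper limit solves (1 - p)^10 = 0.025, so p = 1 - 0.025^(1/10) = 30.8%.
- 3/10: 6.7% to 65.2%.
- Chance of seeing at least one event, 1 - (1 - p)^10: 40.1%, 65.1% and 89.3% for assumed per-child risks of 5%, 10% and 20%.
- Denominator: suppose three children worsen and two of them withdraw before week 4. A paired test on completers sees one worsening child among eight, while a count over all who started remains 3/10.

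**6. Feasibility and workload**

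10/10 completing has a lower limit of 0.025^(1/10) = 69.2%; 8/10 has an interval of 44.4% to 97.5%. Planned sessions are 3 × 4 = 12 per child, and 12 × 10 = 120 in all.

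**The case against.** The strongest reply is that the plan does address tolerability and feasibility. It collects pain linked to the intervention as a separate item, keeps a log during treatment, reports compliance and comments descriptively, and tests the discomfort score. The sentence on means and SDs may even cover compliance. This stands. A reader might infer that the two aims never reach the analysis, or that discomfort during sessions is not collected. The documents support neither reading. What is missing is systematic elicitation, timing and counting.

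A reader might also infer that the plan intends a non-significant VAS result to demonstrate safety. It never says so. The p-value floor above is therefore a caution about interpretation and does not measure the defect. The lack of a safety hypothesis is not a fault either, since none is needed.

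A further objection is that, with N = 10 and no comparator, a count is imprecise and will include background symptoms, given that bone pain is common. This is also true. It argues for recording severity and relatedness, for judging pain against baseline, and for stating the interval. It does not argue for leaving events uncounted.

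**Conclusion.** The concern holds in this form. Safety and feasibility are declared aims, but they are absent from the Objectives and hypotheses. They enter the analysis only through compliance, comments and a pain scale. Because adverse events are not defined, systematically elicited or counted, the trial as written cannot report how many children had one and cannot answer its safety aim. The unnamed VAS item is a smaller wording defect.

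The conclusion rests on the text alone; the VAS changes and event risks used above are assumptions. The 30.8% upper limit for 0/10 comes from the sample size, and the fix does not remove it. The efficacy analyses are not affected.

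**What to change.** - **Objectives.** State safety and feasibility alongside efficacy. No safety hypothesis test is needed.
- **Adverse events (the essential part).** Define them, for example as falls, fractures, and new or worsened pain relative to baseline, with severity and relatedness recorded. Ask about them and record them at every supervised session, covering the interval since the last one, and say who keeps the record. Report the number of children with at least one event, and with at least one intervention-related event, out of all who start a session (withdrawals included), with exact 95% intervals. State that 0/10 excludes only rates above about 31%.
- **VAS.** Record the intervention-associated score at each session and report each child's peak. Restrict the Wilcoxon test to pain at rest, name that item in the SAP, and do not use the result as evidence of safety.
- **Feasibility.** Report children completing the post-assessment out of those enrolled, with an exact interval, and sessions completed out of 12 for each child. Count sessions ended early under adherence, with the reason recorded, so that harm and adherence are not pooled.

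The cost is protocol and SAP wording plus a short question and a VAS at no more than 120 child-sessions. Supervision is already planned, so no extra visits or participants are needed. The downside is a small recording burden and a more modest safety statement.

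### Exclusion 2 misses a child who started a named drug less than 1 month before enrolment, and neither a stability rule nor the analysis deals with medication changes around baseline

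*Combined protocol and SAP*

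**What the plan says.** Exclusion criteria, no. 2, sets a minimum duration and a look-back window: "There is a history of using any of the following medications, regardless of dose, for at least 1 month, within 3 months of enrolment". Two drug classes are named, anabolic agents and growth hormone. Dose is expressly disregarded; duration is not. No reason is given for the 1-month minimum.

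Under Participants, background care carries on: "All participants will continue their usual intervention regime, if any, during the study period". The only behaviour discouraged during the study is other vibration exposure: "They are strongly encouraged not to participate any activities that may involve any total body vibration during the study period".

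Outcome item 4(a) is a "Parental/ participant questionnaire to record present medications of their children". It does not say at which visit it is completed, and it does not ask for start or change dates.

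The sample is small and there is one group: "10 children with type III SMA aged from 6 to 18 years will be recruited". On timing: "Assessments will be performed at baseline and after 4 weeks of the intervention". The Statistical analysis plan uses the Wilcoxon signed test to "compare all the outcome measures listed above (no. 1 to 3) before and after the intervention". Outcome no. 4 is reported descriptively, apart from a before-after test of the pain scale. No comparison is adjusted, split or repeated by medication.

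**The concern.** The protocol does not state the purpose of criterion 2. The natural inference is that it keeps effects of these drugs out of the muscle and bone outcomes. If so, the 1-month minimum leaves a gap where exposure is newest. For example, a child who started 3 weeks before enrolment and continues the usual regime would have about 3 + 4 = 7 weeks of exposure by the final assessment, 4 of them between the two measurements.

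For drugs outside the two classes there is no criterion and no definition of a stable regime. With no comparator, eligibility and recording are the main protection against reading a medication effect as a WBVT effect. The Abstract says the results are meant to inform whether clinicians should recommend the intervention, so a misattributed change could carry beyond the feasibility question.

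**Working it through.** **Who passes criterion 2**

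| Child | Caught by criterion 2? |
|---|---|
| Named class, started 3 weeks before enrolment | No: less than 1 month of use, on any reading |
| Named class, at least 1 month of use inside the window, dose recently changed | Yes: dose is irrelevant |
| Named class, used for 1 month, stopped 11 weeks before enrolment | Depends on the reading |
| Any other drug, recently started or changed | No: not covered |

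The third row is ambiguous. Taking 3 months as about 13 weeks and 1 month as about 4, use ran from week 15 to week 11 before enrolment, so 13 − 11 = 2 weeks fall inside the window. If the full month must lie inside the window, this child is eligible. If any overlap is enough, the child is excluded. The first row does not depend on this.

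**What the analysis would do**

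The plan gives no alpha, power, effect size or SD, so there is no stated figure to reproduce. What follows is an illustration.

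- From the plan: n = 10, one group, signed-rank test of before against after.
- Assumed: two-sided alpha 0.05, exact test without ties, normally distributed changes, true WBVT effect zero, and k of the 10 children with a favourable drug shift of s SD of the change.
- Exact rejection region: smaller rank sum of 8 or less. Of the 2^10 = 1024 sign patterns, 25 give a rank sum of 8 or less in one given direction. The two-sided level is 2 × 25/1024 = 0.0488, and the favourable half is 25/1024 = 2.4%.
- Bias in the mean change: k × s/10 SD.
- Rates from 200,000 simulated trials per scenario:

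| Affected children (k) | s (SD) | Bias in mean change (SD) | False favourable result, per outcome |
|---|---|---|---|
| 0 | – | 0 | about 2.4% |
| 1 | 0.5 to 2 | 0.05 to 0.20 | 3.2% to 4.6% |
| 2 | 0.5 to 2 | 0.10 to 0.40 | 4.2% to 8.7% |
| 3 | 0.5 to 2 | 0.15 to 0.60 | 5.5% to 15.7% |

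With one affected child the total two-sided rejection rate hardly moves (4.78% to 4.95%). The change is mainly in which direction the false results point.

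**Fragility of a single result**

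If the smaller rank sum is 11, p = 2 × 54/1024 = 0.105. Turning the child of absolute rank 3 from decline to improvement gives 11 − 3 = 8 and p = 0.049. The arithmetic is right, but the case is chosen to sit at the threshold. It is not a forecast.

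**Limit on a reduced-sample analysis**

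With 5 children left, the smallest exact two-sided p is 2/2^5 = 0.0625. With fewer it is larger.

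**The case against.** The strongest reply has four parts.

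- *The gap may be empty.* The documents do not say how many of these children take either class, or any other relevant drug. The Abstract calls osteopenia and non-traumatic fractures common, but says nothing about drug treatment. This stands: frequency is unknown.
- *No drug effect is documented.* A reader might infer that a newly started drug would push strength, function and bone density in the direction hoped for from WBVT. The documents give no drug effect on any outcome, in any direction, over 4 weeks. This stands, so the favourable shift above is an assumption.
- *It is partly handled.* Continuing the usual regime suggests unchanged care, and among 10 children drug users can be listed from item 4(a). A reader might conclude that the problem could never be detected afterwards. That is too strong; the accurate statement is that the analysis as planned would not show it. The reply is still incomplete, because usual is not defined as stable and dates are not requested.
- *The root cause is the uncontrolled design.* Growth, practice and changes in therapy confound it too, and this is a feasibility study. True, but that does not justify a duration threshold with no stated reason when removing it costs little.

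Two further inferences fail on the text. One is that the criterion works backwards, excluding past users while admitting current ones; this depends on how the window is read. The other is that any child with a recent drug change gets in. That is wrong for the two named classes once there has been at least 1 month of use inside the window.

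**Conclusion.** The point holds in limited form. Under either reading of the window, a child who started an anabolic agent or growth hormone less than 1 month before enrolment is not excluded by criterion 2. No rule requires other medication to be stable before baseline. The planned analysis would attribute any resulting change to WBVT.

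The likely size is modest. One affected child matters little on average, although the threshold example might tempt a reader to think that one child routinely decides the result. Two or three affected children could matter. These rates rest on an assumed alpha of 0.05, normal changes, no ties and a favourable shift of 0.5 to 2 SD. The repair is worth making because it is specific and cheap, not because a large bias has been shown.

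**What to change.** 1. Remove the 1-month minimum from criterion 2, so that any use of the two named classes within 3 months of enrolment, including current use, excludes. Otherwise state why the minimum is there. Removing it also settles the ambiguity about the window.
2. Use the item 4(a) questionnaire at baseline and at week 4, and add start and change dates for all medications.
3. Prespecify a supportive repeat of each before-after comparison without children who had a relevant drug started or changed between 3 months before enrolment and the final assessment. Read it descriptively: few children may remain, and loss of significance could reflect lost precision alone.

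Which other drugs count as relevant is for the investigators to define in advance. No restriction on any child's care is proposed.

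The cost is one reworded criterion, a questionnaire used at both visits and one extra analysis. The downsides are the possible loss of a recent starter in a rare population and low precision in the supportive analysis. Children on other drugs remain eligible, so for them the change gives transparency, not prevention.
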